We have powerful pilot results showing colonoscopy quality variability in VA and direct association with CRC death.^{23,24} From 1999-2011, 634,331 Veterans had a baseline colonoscopy performed by one of 3101 colonoscopists with ADRs ranging from 13-79%. In patients who had a normal colonoscopy, the higher the provider ADR, the more protected the patient was from developing future CRC: adjusted HR (adjHR) 0.57 for incident (95%CI: 0.42-0.79; ptrend< 0.001) and 0.73 for fatal (95%CI: 0.50-1.06; p=0.047) CRC for the highest vs. lowest ADR quintile. A 5% absolute increase in ADR was associated with relative reductions in fatal CRC risk of 4% after normal colonoscopy (adjHR 0.96, 95%CI: 0.95-0.97). Other important quality metrics, including bowel preparation quality²⁵⁻²⁸ and cecal intubation rate¹⁶ also impact patient outcomes. Both poor bowel preparation and incomplete examinations, for example, are associated with missed lesions²⁹ and need for earlier repeat procedures.

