We will construct a mixed effects generalized linear model that will act on data aggregated monthly within each provider to estimate the average intervention effect across providers. We will use a Poisson outcome model with a log link to characterize each provider’s monthly rate, where the number of positive screens will be the outcome and the log of the number of total screens will be included as an offset term.^{53,54} In the case of over-dispersion, we will use a negative binomial outcome model. The main predictor of interest will be a pre/post indicator for whether the report card intervention was in effect at a particular month (Intervention). We will additionally control for time since the study began in quarters (Time, coded as a categorical variable) to account for secular trends; as well as site level characteristics obtained from administrative and the quantitative survey data (Aim 1) (urban/rural, cumulative annual procedure volume in 2018 and current volume, site annual ADRs in 2018, use of split dose bowel preparation protocols (SDBP) in 2018, and whether or not ADR was measured in 2018), provider level characteristics (baseline years in practice, primary practice type {academic, hospital employed, private practice}, and baseline annual procedure volume), and baseline patient characteristics aggregated to the provider level (age, sex, race/ethnicity). Since study time will be coded in quarters, it will incorporate seasonal effects in addition to secular trends over the study period. Random effects will be included for both provider and site, where provider is nested within site. Let $PositiveScreens_{ijt}$ denote the observed number of positive screens for the j th provider at site i during month t , and let $TotalScreens_{ijt}$ denote the total number of patients screened. Because the monthly screening rates are expected to be relatively low (≤ 0.30), we assume that the observed number of positive screens, $PositiveScreens_{ijt}$ follows a Poisson distribution with conditional mean λ_{ijt} . We anticipate the following model for λ_{ijt} on a log scale, where $TotalScreens_{ijt}$ is included as an offset term on the right hand side of the equation: $\text{Log}(\lambda_{ijt}) = \beta_0 + \beta_1 Intervention_{ijt} + \beta_2 Time_{ijt} + \beta_3 Urban_i + \beta_4 SiteVolume_i + \beta_5 YrsPractice_{ij} + \beta_6 PracticeType_{ij} + \beta_7 ProviderVolume_{ij} + \beta_8 Age_{ij} + \beta_9 Sex_{ij} + \beta_{10} Race_{ij} + \beta_{11} Volume2018_i + \beta_{12} ADR2018_i + \beta_{13} SDBP2018_i + \beta_{14} ADRMeasured_i + \alpha_i + \mu_{j(i)}$, where β_0 is the intercept, β_2 is a vector of coefficients for the study quarter as expressed by $Time_{ijt}$, α_i indicates the random effect for site i , $\mu_{j(i)}$ indicates the random effect for provider j within site i . $Volume2018_i$ (high/low), $ADR2018_i$ (high/low) and $ADRMasured_i$ (yes/no) are the indicator variables used in stratifying the baseline randomization of sites to waves. We will also examine whether the intervention effect varies by time since intervention and by provider characteristics by considering these interaction terms in the model. Under the proposed Poisson model and logarithmic link function, exponentiating the results will allow us to report rate ratios (RRs), their 95% confidence intervals (CIs), and p-values from the models. Under the generalized linear mixed model the estimated treatment effect, obtained by exponentiating the estimate of β_1 , represents the ratio of the screening rate after versus before implementing the intervention for a given provider.

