
We will plot monthly ADRs for a random sample of endoscopists to examine how the ADR rate changes over time, and to check for the presence of a lagged intervention effect. We expect to see about a one month lag in the intervention effect and plan to drop the outcome data for this period to avoid biased estimates.⁵⁵ We will

examine correlation between successive monthly ADR rates within providers using residual plots and the Durbin-Watson or Durbin's alternative test and include study time lags as appropriate.⁵⁶ If these analyses suggest that the residual covariance deviates substantially from those assumed by the nested random effects model, we will substitute a generalized estimating equation (GEE) analysis under the assumption that outcomes are independent between sites, and use robust standard errors for statistical inference.⁵⁷ The GEE approach can also be used as a fallback if the nested random effect structure of the generalized linear mixed model turns out to be numerically intractable. [As a secondary question we will assess the impact of compliance with the intervention on ADR rate among the providers from Aim 2 who responded to our survey. Compliance will be measured in Aim 1 by dashboard access and participation in one or more collaborative learning sessions. Compliance will be modeled as an interaction with intervention in the model described above, to see if the efficacy of the intervention varies by compliance status.]

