Power Calculation: Our power calculation for the intervention effect comes from a stepped wedge model. Based on 2017 data there were 73 sites with 657 providers performing 155,926 cases per year in our sampling frame. We estimate a 5% loss of site data due to data quality issues. We also estimate a provider attrition rate of 8% from four years of data provided by the national GI program office where attrition rates ranged from 6.9-12%.¹⁵ After accounting for data loss and provider attrition, we expect 69 sites with 571 providers seeing 135,517 patients/year, corresponding to 95 providers/wave and 59 patients/provider/quarter. Note that the number of patients seen by providers factors into our power calculation as it affects the standard errors of the intervention effect, where seeing more patients yields greater power. Our primary outcome is ADR, which we will conservatively estimate as having a range of 13-79% based on prior research^{7,8} and our preliminary data. For cluster randomized trials using implementation designs such as ours, the intra-cluster correlation coefficient (ICC) estimates for patient outcomes are approximately 0.030.⁵⁸ Based on an ADR of 27.5% in the pre-intervention period, we would have about 93% power to detect a 1.0% absolute increase in ADR. This difference is clinically important, because a 1% increase in ADR is associated with a 3.0% decrease in risk of incident CRC, and a 5% decrease in risk of fatal interval CRC.⁷ Power calculations were conducted in R using the swCRTdesign package, and are conservative due to exclusion of three quarters of baseline data, and because the second level of clustering by provider is not considered.^{59,60}

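### Model-based Poisson standard errors are unreliable for a yes/no outcome: up to about 17% too large at 27.5% ADR, with robust standard errors only a conditional fallback

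*Combined protocol and SAP*

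**What the plan says.** Under Outcome measures, ADR is the percentage of patients with at least one adenoma, so each colonoscopy contributes a yes or a no to a known total. The Primary Analysis section (Stepped Wedge at the Provider Level) models the provider-month count of positives with a log link, an offset for the number screened, quarter as a categorical term, and random intercepts for site and for provider within site. The distribution is justified as follows: "Because the monthly screening rates are expected to be relatively low (≤ 0.30), we assume that the observed number of positive screens" is Poisson. On inference the section says that "exponentiating the results will allow us to report rate ratios (RRs), their 95% confidence intervals (CIs), and p-values from the models".

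Two provisions cover departures from the model:

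- "In the case of over-dispersion, we will use a negative binomial outcome model".
- After residual plots and Durbin-type tests of successive monthly rates, if the residual covariance departs substantially from the nested model, "we will substitute a generalized estimating equation (GEE) analysis under the assumption that outcomes are independent between sites", with robust standard errors. "The GEE approach can also be used as a fallback if the nested random effect structure" proves numerically intractable.

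The Power Calculation that follows takes a pre-intervention ADR of 27.5% and states that "we would have about 93% power to detect a 1.0% absolute increase in ADR". The same paragraph says of ADR that the authors "conservatively estimate as having a range of 13-79"%, and the Background reports "3101 colonoscopists with ADRs ranging from 13-79"%. The Explanatory Analysis repeats the Poisson model on individual patients, without an offset, and mentions no robust standard error.

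**The concern.** A Poisson count with mean np has variance np; a binomial count has np(1−p). The two nearly agree only when p is small, and 0.275 to 0.30 is not small for this purpose. The confidence interval and p-value of the primary rate ratio therefore rest on a variance that a yes/no outcome does not have.

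Neither safeguard is aimed at this. A negative binomial can only raise the variance above Poisson. The switch to GEE depends on correlation between months or on a fitting failure, not on a check of the variance function. Variance below Poisson is what binary data show at this rate when there is no extra variation, and it has no named remedy.

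At stake are the width of the primary interval, the true size of the test, and the power for a 1-point gain that the plan calls clinically important. The error could also run the other way. With intercepts only for site and provider, variation of a site's ADR from quarter to quarter is left out, and the same standard error could be too small.

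**Working it through.** **Inputs.** From the Power Calculation: ADR 27.5%, effect +1.0 point, ICC 0.030, 69 sites, 571 providers, 135,517 patients a year. Six quarterly waves come from the design section. Two-sided α = 0.05 is assumed from the 95% intervals, because no α is stated for the power figure. Patients per site-quarter: 135,517/69/4 = 491. Patients per provider-month: 135,517/571/12 = 19.8.

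**1. Reproducing the stated power.** A Hussey-Hughes calculation used waves of 12/12/12/11/11/11 sites, residual variance p(1−p), and 11 quarters (one baseline, six steps, four follow-up; this is a reading of the plan's remark that three baseline quarters were excluded). It gives SE 0.00288 and power 93.4%. The plan's 93% thus reproduces with binomial variance, which is not the variance of the planned analysis.

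**2. Size of the overstatement.** SE ratio (Poisson/binomial) = 1/√(1−p).

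| ADR | SE ratio |
|---|---|
| 13% | 1.07 |
| 27.5% | 1/√0.725 = 1.174 |
| 30% | 1.195 |
| 50% | 1.41 |
| 79% | 2.18 |

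**3. Test size at 27.5%.** 2 × [1 − Φ(1.96 × 1.174)] = 2.1%.

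**4. Power when only the reported SE is inflated.** 93% power corresponds to 1.476 + 1.960 = 3.436 standard errors. Φ(3.436 − 1.96 × 1.174) = Φ(1.13) = 87%. In the stepped-wedge calculation:

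| Design | Binomial SE | Poisson SE |
|---|---|---|
| 11 quarters | 93.4% | 87.8% |
| 14 quarters | 95.0% | 90.4% |
| 14 quarters, roll-out quarter dropped | 84.5% | 75.0% |

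The fall from the second row to the third comes from discarding the roll-out quarter and is a separate matter. Only the difference across each row concerns the standard error.

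**5. Direction.** With provider-month ICC ρ, true variance over Poisson variance is (1−p)[1 + (n−1)ρ]. Setting this to 1 with n = 19.8 gives ρ = (1/0.725 − 1)/18.8 ≈ 0.020. Below that the Poisson SE is too large; above it, too small (about 6% too small at ρ = 0.03).

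**6. Simulation.** Provider-month data for 571 providers in 69 sites over 42 months, mean 19.8 patients, roll-out quarter dropped, site ICC 0.03, provider SD 5 points (assumed). The fit was a log-link Poisson model with quarter terms and profiled provider intercepts in place of the nested random intercepts, and no other covariates. Robust SEs were clustered by site with a Kauermann-Carroll-type correction and t on 68 df. The ICCs in the second and third rows are assumptions, not figures from the documents.

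| Residual variation | Null rejection, model-based | Null rejection, robust |
|---|---|---|
| Binomial only | 1.9% (2,200 runs) | 4.6% (1,200 runs) |
| Provider-month ICC 0.02 | 4.6% (800 runs) | 4.4% |
| Site-by-quarter ICC 0.0015 (SD 1.7 points) | 8.2% (1,000 runs) | 5.4% |

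The ratio of model-based to true SE was 1.04 in the second row and 0.89 in the third. Shorter runs of 200 to 250 trials gave 1.16 and 1.21 with binomial residuals, and 0.94 at the same site-by-quarter ICC. Pearson dispersion was 0.73 (binomial only) and 0.75 (site-by-quarter), so the over-dispersion rule would not act in either. For a true +1 point with binomial residuals (600 runs), power was 72% model-based and 83% robust. Monte Carlo error is about 0.3 to 0.9 points for null rejection and 1.6 to 1.8 points for power.

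**The case against.** The strongest reply is that the only effect due to the Poisson choice itself is conservative: type I error falls, the rate ratio is not shown to be biased, and the cost is some precision. The 17% is also a ceiling. A provider-month ICC near 0.02 removes it, and the documents do not say what that ICC is. Both points stand, and they limit the claim to an error of unknown sign whose upper bound is 17% at 27.5%.

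The narrow-interval scenario is, strictly, a missing random effect and would trouble a binomial mixed model with the same intercepts. It also rests on an assumed variance. That stands too, but it is a further reason not to rely on a model-based standard error, and the same remedy deals with it.

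Residual covariance could be read broadly enough to include variance, so the GEE might start anyway. The planned checks were not simulated, so this is not excluded. However, the text ties the trigger to correlation between successive months and gives no rule for variance below Poisson.

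The 0.30 bound may describe typical rates, which 27.5% fits. The 13-79% range is a minimum and maximum and does not show how many providers lie above 0.30. This part is a wording matter, and the argument does not need it: at 0.30 the excess is already 20%.

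Finally, the simulations stand in for the planned model and do not fit it exactly. The 1/√(1−p) result does not depend on them.

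**Conclusion.** The concern holds. With binomial residual variation at 27.5% ADR, the planned standard error is about 17% too large, the 5% test runs at about 2%, and 93% power becomes about 87%. These figures assume a two-sided 5% test and no extra variation beyond the intercepts and quarter terms. With extra variation the error shrinks and can reverse; the 8.2% null rejection depends on the assumed site-by-quarter ICC of 0.0015. Because the documents give neither variance, the model-based interval and p-value cannot be relied on in either direction. The estimated rate ratio is not called into question. No model is stated for cecal intubation or bowel preparation, so the point reaches those outcomes only if this model is used for them. The matter should be fixed before analysis, and the remedy is already named in the plan as a fallback.

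**What to change.** Keep the log-link Poisson mean model and the rate ratio. Prespecify site-clustered robust (sandwich) standard errors as the default for the primary analysis, with a small-sample correction and a t reference suited to about 69 sites. Apply the same rule to the patient-level Poisson re-analysis, and to the secondary outcomes if they use this model. Delete the 0.30 justification or reconcile it with the 13-79% range.

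The cost is SAP wording and one model option; no new data are needed. There are two small drawbacks. Without the small-sample correction, robust standard errors were slightly too small (null rejection 6.4% in 1,000 runs), so the correction should be named. If the model is fitted by GEE, the rate ratio becomes population-averaged, and the plan's description of it as the effect for a given provider must change accordingly.

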[Analysis Overview: Our goal is to compare the efficacy of VA-EQuIP versus usual care for the primary outcomes of overall (all indications) and screening indication ADR and secondary outcomes of bowel preparation quality and cecal intubation rate. We hypothesize that VA-EQuIP will lead to a higher rate of ADR, bowel preparation quality and cecal intubation relative to standard of care. We also hypothesize the effect will be particularly pronounced among providers who have low ADR, bowel preparation quality and cecal intubation rates prior to our intervention. The primary analysis takes advantage of the stepped wedge design by simultaneously comparing pre- and post- intervention data both within and across providers to evaluate the effect of the intervention while controlling for secular trends, which are uniform across sites. As a secondary analysis, we will implement a two-stage interrupted time-series and meta-regression analysis, which is commonly used to study intervention effects when an intervention occurs at different times within different providers. For all analyses, our primary inferences evaluate the ratio of ADR with versus without intervention for a given provider. However, our planned analyses also address the data structure, which nests patients within providers within sites.]

Eligibility / Inclusion criteria: We have identified 73 VA sites spanning VA (**Figure 4**) eligible for the study that have endoscopists with colonoscopy procedure and pathology notes in our database (SCS_Endoqual). In 2017, these 73 sites had 657 providers performing 155,926 colonoscopy procedures. The point of contact (i.e. GI section chief) at each site will be contacted by email about planned VA-EQuIP implementation and given specific instructions for accessing site data.

Exclusion criteria: VA facilities without existing colonoscopy procedure or pathology notes in our operational database will not be included in the study.

Consent: The national GI program office will implement VA-EQuIP as an operational initiative. We will obtain provider verbal consent by telephone, if deemed necessary by the IRB, for the evaluation.

Figure 4: VA-EQuIP sites

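### The stepped-wedge tests of effect modification and compliance share one set of quarter effects, so a between-group difference in secular trend is read as a difference in the VA-EQuIP effect

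*Combined protocol and SAP*

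**What the plan says.** All references are to Aim 1 of the combined protocol and SAP.

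- **Time adjustment** (Primary Analysis). The model will "control for time since the study began in quarters (Time, coded as a categorical variable) to account for secular trends". In the equation, the Time coefficient "is a vector of coefficients for the study quarter as expressed by" the Time variable. There is one such vector for all providers. The random effects are intercepts for site and for provider within site.
- **Effect modification** (same section). The plan will examine whether the effect differs with time since crossover and "by provider characteristics by considering these interaction terms in the model". It does not list which characteristics.
- **Compliance** (same section). "Compliance will be modeled as an interaction with intervention in the model described above". It is measured by dashboard access and session attendance, among survey respondents.
- **Hypothesis** (Analysis Overview). "We also hypothesize the effect will be particularly pronounced among providers who have low ADR", with the same expectation for bowel preparation and cecal intubation.
- **Stated assumption** (Analysis Overview). The design is described as "controlling for secular trends, which are uniform across sites".

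No term for time by characteristic or time by compliance appears. The GEE fallback changes how correlation is handled and adds no group-specific time terms. The patient-level repeat under Explanatory Analysis is described as very similar.

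**The concern.** The strength of a stepped wedge is that, in the same quarter, sites that have crossed over are compared with sites that have not. With one shared set of quarter effects, the interaction hardly uses that comparison. The quarter effects remove only the average trend. What remains is each group's own departure from it, and because exposure is nearly synonymous with later calendar time, that departure loads on the interaction. Stratified randomisation of sites does not help, because the compared groups (low against high performers, compliers against non-compliers) were not randomised.

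This is distinct from regression to the mean: it would arise even if groups were defined on independent 2018 data.

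At stake are a declared hypothesis (low performers gain most) and a named secondary question (whether efficacy depends on compliance). The Next Steps section also looks to this evaluation when considering more intensive interventions for persistently low performers.

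**Working it through.** **1. The plan's own figure.** The only power statement for this model concerns the overall effect: "Based on an ADR of 27.5% in the pre-intervention period, we would have about 93% power to detect a 1.0% absolute increase in ADR". Inputs from Power Calculation: 69 sites, 135,517 patients a year (135,517 / 4 / 69 = 491 per site-quarter), ICC 0.030, one baseline quarter. Added: six steps, four follow-up quarters and, by assumption, two-sided 5%. A random-intercept model with categorical quarters gives a standard error (SE) of 0.290 point and 93.2% power, so the figure reproduces. It does so only if the implementation quarter counts as exposed. Dropping that quarter, as the plan intends, gives 80.9%. That is a separate matter. The checks below drop the quarter.

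**2. How much trend leaks.** Figure 5 gives 14 quarters: 4 baseline, 6 steps, 4 follow-up. A wave has p months before and q after, with p + q = 39 and 3 dropped between. The distance between the midpoints is p/2 + 3 + q/2 = 19.5 + 3 = 22.5 months = 1.875 years, the same for every wave.

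With equal groups spread evenly over waves, take the difference between group means in each wave and quarter. Shared quarter effects cancel, and the interaction becomes the post-minus-pre change in that difference:

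false interaction = trend gap per year × 1.875

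- 0.25 point/year: 0.25 × 1.875 = 0.47 point
- 0.5 point/year: 0.5 × 1.875 = 0.94 point

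A random-intercept fit gives 0.468 and 0.935. At 0.5 point/year it reads −0.47 and +0.47 in the two groups when both true effects are zero.

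**3. SE as planned.** With 571 providers and 59 patients per provider-quarter, the cell variance is 0.275 × 0.725 / 59 = 0.00338. With 571 / 12 = 47.6 providers per wave and group, the difference has variance 2 × 0.00338 / 47.6 = 0.000142. Information over waves is Σ pq/(p+q) in quarters = 2 × (36 + 40 + 42)/13 = 18.15. SE = √(0.000142 / 18.15) = 0.0028, or 0.28 point (0.279 in the fit). For a 20/80 split, multiply by √(6.25/4) = 1.25, giving 0.349.

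**4. Rejection with no true effect**, Φ(bias/SE − 1.96):

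| Assumed gap (points/year) | Bias | 50/50 | 20/80 | 50/50 with group × quarter |
|---|---|---|---|---|
| 0 | 0 | 5% | 5% | 5% |
| 0.25 | 0.47 | 39% | 27% | 5% (bias 0.00) |
| 0.5 | 0.94 | 92% | 76% | 5% (bias 0.00) |
| 1.0 | 1.87 | about 100% | about 100% | 5% (bias 0.00) |

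These use binary variance. Model-based Poisson SEs are wider by √(1/0.725) = 1.17, so the critical value is 1.96 × 1.17 × 0.279 = 0.643 point. Rejection is then Φ((0.468 − 0.643)/0.279) = 27% and Φ((0.935 − 0.643)/0.279) = 85%. The bias itself is unchanged: a log-link version gives false interaction rate ratios of 1.017 and 1.034.

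The compliance test uses survey respondents only. At the 69% response of the earlier needs-assessment survey (an assumption here), SE = 0.279/√0.69 = 0.336, and 39% and 92% become 28% and 79%.

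**5. Price of the correction** (50/50):

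| Time terms | SE (points) | Power for a 1.0-point difference |
|---|---|---|
| Shared quarters (plan) | 0.28 | 95% |
| Group × linear time | 0.57 | 42% |
| Group × quarter | 0.67 | 32% |

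With group × quarter terms, the difference detectable with 80% power is about 1.9 points, against about 0.8 as planned.

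**The case against.** **Not all planned analyses are affected.** A reader might infer that every look at effect heterogeneity is compromised. The documents do not support that. The secondary interrupted time-series analysis gives each provider its own linear trend before pooling, and a linear trend gap produced zero bias in its level change in all six waves. It is only a partial check. Its second-stage covariates are listed as adjustment, its 2018 ADR variable is at site level, it has no compliance term, and the plan concedes that it lacks concurrent controls. The time-since-intervention interaction does not compare groups of providers, so it is also outside the point.

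**The trend gap is assumed.** A reader might infer that the low-performer hypothesis will be falsely confirmed. Nothing in the documents shows that low and high performers drift apart, and uniform trends are an openly declared assumption. That stands: the bias is conditional. But the declared assumption concerns sites, not groups of providers within them, and no check of it is planned. For compliers, who select themselves by opening dashboards, attending sessions and answering the survey, a common trend cannot be presumed.

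**The tests are secondary and the remedy is expensive.** No error rate, power or decision rule rests on them, and precision falls 2.4-fold. This also stands. It argues against making the corrected model the sole basis for all claims, which is a choice between bias and variance. It does not argue against fitting it.

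**The overall effect.** A reader might infer that the primary result is biased too. It is not biased by this route: randomisation, stratified by site volume and ADR, spreads the groups over waves.

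**Conclusion.** The point holds for the between-group interactions in the stepped-wedge model (intervention by provider characteristic, intervention by compliance) and for their patient-level repeat. About 22.5 months of any linear trend gap passes into the interaction. The mechanism follows from the model as written. Its size depends on a gap that the documents do not give: 0.25 to 0.5 point per year yields 0.47 to 0.94 point, the upper value being nearly the whole 1.0-point effect for which the trial is powered. Rejection of about 39% to 92% further assumes equal groups spread evenly over waves, all 571 providers, an ICC of 0.030, binary variance and two-sided 5% tests. Unequal groups, fewer respondents or Poisson SEs lower it. If trends are in fact equal, the planned tests are valid and more precise. The change is worth making because it is cheap and protects a declared hypothesis and a named secondary question.

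**What to change.** In the Primary Analysis section, and for the patient-level repeat:

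- **Provider characteristics.** Fit each intervention-by-characteristic interaction also with characteristic-by-quarter terms (or characteristic-by-linear-time). Report it beside the planned version, and claim effect modification only if this model does not contradict it.
- **Compliance.** Make the compliance-class-by-time model the main one and keep the planned version as supportive. Define class in a fixed window after each wave's T(0). Since all sites cross over, eventual compliers already exposed can then be compared with eventual compliers still waiting.
- **State the limit.** Class is seen only for survey respondents still present after their wave's T(0), which falls 15 months later in wave 6 than in wave 1. With 8% provider attrition assumed in the power calculation, compliers may be selected differently by wave.
- **State the precision.** For equal groups, the interaction SE rises from about 0.28 to 0.67 point (0.57 with linear time), and power for a 1.0-point difference falls from about 95% to 32% (42%). A null result from the corrected model is therefore weak evidence of no difference.

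The cost is SAP wording and extra model fits, with no new data. No stated power is lost, since none is claimed for these tests.

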rates for 2018 will be used to determine randomization strata (high vs. low ADR). Our stepped wedge design yields varying pre- and post-intervention periods for each enrollment wave or “cluster” (Figure 5).

New sites will be enrolled quarterly in 6 waves (12-13 wave, 73 total). For each wave, we will discard the data from the 3-month period where the intervention is being implemented. We will augment baseline data capture by 12 months and we will extend data capture following our final wave by another 12 months to improve estimation of pre/post intervention effects within individual providers who are members of the first and final waves. Under this design, both the pre- and post-intervention data available will range from 12-27 months depending on the wave, with an average of 19.5 months of data.

Clusters	Jan 2019	Jan 2020	Apr 2020	Jul 2020	Oct 2020	Jan 2021	Apr 2021	Jul 2021	Jun 2022
	Baseline 1yr	Step 1	Step 2	Step 3	Step 4	Step 5	Step 6		Follow-up 1yr
1	○	X	○	○	○	○	○	○	○
2	○	○	X	○	○	○	○	○	○
3	○	○	○	X	○	○	○	○	○
4	○	○	○	○	X	○	○	○	○
5	○	○	○	○	○	X	○	○	○
6	○	○	○	○	○	○	X	○	○

X –VA-EQuIP Intervention ○ – Measurement Collected

Figure 5: Enrollment Strategy for Stepped Wedge Trial Design

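### The fallback GEE for the primary analysis names no small-sample correction, reference distribution or working correlation; with about 69 sites and 28 coefficients, a classical robust z test would reject about 5.4-11% of the time under no effect

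*Combined protocol and SAP*

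**What the plan says.** The Aim 1 primary analysis (Primary Analysis -- Stepped Wedge at the Provider Level) is a Poisson mixed model with random intercepts for site and for provider within site. After the residual checks, the same section allows a GEE to take its place in two situations. One is covariance misfit: "If these analyses suggest that the residual covariance deviates substantially from those assumed by the nested random effects model". The other is numerical failure: "The GEE approach can also be used as a fallback if the nested random effect structure" of the mixed model cannot be fitted. The GEE is to be run "under the assumption that outcomes are independent between sites, and use robust standard errors for statistical inference". Nothing more is said about its variance estimator, working correlation or reference distribution.

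The number of independent units comes from the Aim 1 Power Calculation: "we expect 69 sites with 571 providers seeing 135,517 patients/year, corresponding to 95 providers/wave and 59 patients/provider/quarter". The number of coefficients comes from the model equation, including the time adjustment: "We will additionally control for time since the study began in quarters (Time, coded as a categorical variable" and so on. Rollout is described as "New sites will be enrolled quarterly in 6 waves (12-13 wave, 73 total" sites, and for each wave "we will discard the data from the 3-month period where the intervention is being implemented".

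**The concern.** The classical sandwich variance is justified as the number of clusters grows large relative to the number of coefficients. Here the clusters are sites, about 69 of them, and the model uses about 28 coefficients, six of them for site-level terms. Residuals from a model that rich are too small, so the robust standard error is on average too small and a z test rejects too often.

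Once substituted, the GEE supplies the rate ratio, confidence interval and p-value for the primary outcomes, overall and screening ADR. The plan does not say how large a covariance departure triggers the switch. The mixed model has only random intercepts, while the plan itself intends to look for serial correlation and for variation in effect across sites and providers, so the switch is a real possibility. The details that set the error rate would then be chosen after the data had been examined.

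**Working it through.** **Inputs from the documents.** 69 sites, 571 providers, 59 patients per provider per quarter, ICC 0.030 and ADR 27.5% (Power Calculation). Six quarterly waves with the implementation quarter dropped. Four quarters of 2019 plus 30 prospective months: 4 + 10 = 14 quarters. The 5% two-sided level is inferred from the 95% confidence intervals.

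**Coefficient count from the model equation.** Intercept 1, intervention 1, quarters 14 - 1 = 13. Six site terms: urban, site volume, 2018 volume, 2018 ADR, 2018 split-dose preparation, ADR measured. Seven provider or patient terms: years in practice 1, practice type 3 - 1 = 2, provider volume 1, age 1, sex 1, race 1. Total 1 + 1 + 13 + 6 + 7 = 28. Race as one coefficient makes this a minimum. Sites minus parameters: 69 - 28 = 41.

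**The plan's own figure.** The documents give no error rate for the fallback. Their power figure serves to check the design inputs. Patients per site-quarter: 571/69 x 59 = 488. The Hussey-Hughes variance, with between-site variance 0.03/0.97 x 0.275 x 0.725 and 1 + 6 + 4 = 11 quarters, gives SE 0.00289 for the 0.010 difference and power of 93.3%, matching the stated 93%. That match needs the implementation quarter to be kept; dropping it gives SE 0.00352 and 81%. This is a separate matter.

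**Assumptions not in the documents.** Main simulation: 3,000 null trials per scenario; site-size CV 0, 0.6 or 0.9; site and provider SDs of 0.2 each on the log scale. The combined SD is sqrt(0.04 + 0.04) = 0.283, and (0.275 x 0.283)^2 / (0.275 x 0.725) = 0.030, the plan's ICC. Some scenarios add site-by-quarter variation (SD up to 0.12), site slopes (SD 0.15) or site-level effect heterogeneity (SD 0.1, mean zero). Provider-quarters stand in for provider-months.

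**Results, 28 coefficients, classical sandwich, z test.** If the standard error is too small by a ratio r, the rejection rate is roughly 2 x Phi(-1.96 r). The nested row is from 2,000 datasets with site SD 0.28, provider SD 0.25, providers-per-site CV 0.6 and provider-volume CV 0.8.

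| Working correlation, site sizes | Mean SE | Empirical SD | r | 2 x Phi(-1.96 r) | Simulated |
|---|---|---|---|---|---|
| Independence, equal | 0.0479 | 0.0524 | 0.914 | 7.3% | 7.6% |
| Independence, CV 0.6 | 0.0507 | 0.0601 | 0.844 | 9.8% | 10.4% |
| Independence, CV 0.9, site slopes | 0.0520 | 0.0629 | 0.827 | 10.5% | 11.1% |
| Exchangeable, equal | 0.0117 | 0.0121 | 0.967 | 5.8% | 6.5% |
| Exchangeable, CV 0.6 | 0.0140 | 0.0153 | 0.915 | 7.3% | 8.2% |
| Exchangeable, CV 0.9, site slopes | 0.0153 | 0.0169 | 0.905 | 7.6% | 8.8% |
| Nested exchangeable, CV 0.6, site autocorrelation 1.0 | 0.0117 | 0.0120 | 0.975 | 5.6% | 5.4% |

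Across all main scenarios the range is 7.6-11.1% (independence) and 6.3-8.8% (exchangeable). Nested exchangeable gave 7.3% at site autocorrelation 0.95. A further set of 1,500 datasets per scenario gave 8.7% (independence), 7.3-7.7% (exchangeable) and 6.2-7.5% (nested exchangeable). Monte Carlo error is about 0.4-0.6 points in the main and 2,000-dataset runs.

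**Role of the covariates.** With only the intercept, intervention and quarters (1 + 1 + 13 = 15 coefficients), the main simulation still gives 6.1-7.6% (independence) and 6.4-6.8% (exchangeable).

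**Effect of correction, 28 coefficients, main simulation.**
- Changing only the reference to t(41): 6.8-10.1% (independence), 5.5-8.4% (exchangeable).
- Kauermann-Carroll with t(41): 5.1-6.7% and 4.9-6.7%. The 1,500-dataset runs gave 4.7-6.1%.
- Mancl-DeRouen with t(41): 3.3-4.2% and 4.0-5.1%.

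**Why the working correlation matters.** The planned effect is ln(28.5/27.5) = 0.036. With an independence SD of 0.0524-0.0674, power is about 8-10%; the exchangeable SDs in the table are 0.012-0.017.

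**The case against.** The plan does not say that its robust standard errors are uncorrected. That is inferred from silence, and a cited source might specify a correction. This stands as a limit on the wording. It does not remove the need to state the estimator, since the unqualified term ordinarily means the classical sandwich.

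A reader might infer an error rate of 8-11%. The documents do not support that. Its upper part needs working independence, and the plan's assumption of independence between sites defines the cluster without choosing that structure. Independence would also leave very little power for the planned effect, so a sponsor would have good reason to avoid it. The structure closest to the planned model, providers nested within sites, gave 5.4% in its most favourable case, where the random-intercept covariance is correct. In that case, however, the covariance trigger should not fire; with autocorrelation 0.95 the rate was 7.3%.

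A reader might also blame the covariate list alone. The 15-coefficient runs show inflation without it, and under nested exchangeable at autocorrelation 1.0 the covariates made no difference (5.6% without, 5.4% with).

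Finally, this is a conditional analysis. Nothing here counts against the mixed model itself.

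**Conclusion.** The point holds as a gap in the fallback specification with a modest but real consequence. If the GEE replaces the mixed model and is run with a classical sandwich and z test, the nominal 5% test would reject about 5.4-11% of the time under no effect: about 7.6-11% for independence, 6-9% for exchangeable and 5-7.5% for nested exchangeable. The size rests on assumed site-size variation and variance components; equal site sizes bring the exchangeable figure down to 6.3-6.5%. The 69 sites and the count of 28 come from the plan. The larger uncertainty is the unnamed working correlation, which affects both the error rate and, far more, the precision.

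**What to change.** Where the primary analysis section introduces the GEE, state that it will use an exchangeable or nested-exchangeable (provider within site) working correlation rather than independence, with sites as clusters; a bias-corrected sandwich, naming either Kauermann-Carroll or Mancl-DeRouen; and a t reference on sites minus parameters degrees of freedom (41 with 69 sites and 28 coefficients). Changing the reference distribution alone is not enough. Of the two corrections, Mancl-DeRouen was slightly conservative in places and Kauermann-Carroll slightly liberal; either is acceptable if chosen in advance.

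The cost is one sentence in the plan and a slightly wider confidence interval if the fallback is used. No new data or design change is needed.
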